PARTNERS HUMAN RESEARCH COMMITTEE PROTOCOL SUMMARY

Answer all questions accurately and completely in order to provide the PHRC with the relevant information to assess the risk-benefit ratio for the study. Do not leave sections blank.

PRINCIPAL/OVERALL INVESTIGATOR

[name]

PROTOCOL TITLE

Development and Implementation of Electronic Decision Aids for Genetic Testing in Inherited Cancer Syndromes

FUNDING

NIH U01CA243695-01

VERSION DATE

11/3/2022 (V3.0)

SPECIFIC AIMS

Concisely state the objectives of the study and the hypothesis being tested.

We propose to implement an electronic decision aid to assist individuals in choosing a multi-gene panel with their medical oncologist instead of a genetic counselor. We will test the hypothesis that a decision aid without a genetic counselor can facilitate quality decisions around the selection of a specific multi-gene panel. In addition to positive changes in knowledge, shared decision making, and decisional conflict, we anticipate that the decision aid will increase access to genetic testing in a timely manner. Utilizing an effectiveness-implementation hybrid study design, we propose these specific aims:

1. To pilot electronic decision aids for selection of a multi-gene panel
 - a) Implement our decision aid already completed for ovarian cancer patients
 - b) Adapt the decision aid for pancreatic cancer patients
 - c) Create standard operating procedures for implementation and pilot each tool at two institutions (MGH and BMC) to establish feasibility and acceptability

BACKGROUND AND SIGNIFICANCE

Provide a brief paragraph summarizing prior experience important for understanding the proposed study and procedures.

The indications and demand for genetic testing in cancer care are rapidly growing. Hereditary cancer syndromes are more common than previously appreciated, and genetic testing is standard of care to establish these diagnoses. In addition, genetic test results are now critical to guiding targeted therapies in patients with established tumors such as ovarian and pancreatic cancer, so timely access to genetic testing is essential. Genetic counselors have traditionally managed the testing process, but there is a critical shortage of counselors and they are not able to meet the demand for testing. Without a genetic counselor, effective communication of testing options, outcomes, and risks could be compromised. Oncologists are unable to offer testing by themselves due to lack of time and expertise in genetic testing. One of the most challenging decisions in the pre-test setting is the choice of gene panel. Multi-gene panels are now the norm, but panels can include as few as 5 or as many as 125 genes. This variation depends upon whether the panel includes genes associated with a single tumor type or multiple tumor types, and whether genes with low levels of evidence of pathogenicity are also included. There is no consensus on what constitutes an ideal panel, and the decision of which panel to select is highly individualized. Innovative strategies to support patients facing these time-sensitive and complex pre-test decisions are needed.

Decision aids are well-suited to address this challenge by providing education, facilitating the process of informed choice, clarifying personal preferences, and promoting shared decision making.

RESEARCH DESIGN AND METHODS

Briefly describe study design and anticipated enrollment, i.e., number of subjects to be enrolled by researchers study-wide and by Partners researchers. Provide a brief summary of the eligibility criteria (for example, age range, gender, medical condition). Include any local site restrictions, for example, “Enrollment at Partners will be limited to adults although the sponsor’s protocol is open to both children and adults.”

All adult patients diagnosed with malignant ovarian tumor or malignant pancreatic adenocarcinoma who are referred for genetic testing and who have not previously completed germline genetic testing will be invited to complete the Decision Aid at the start of their next clinic appointment. Patients who are unable to complete surveys will be excluded from this study.

We plan to enroll 100 patients in total (50 ovarian cancer patients; 50 pancreatic cancer patients) between MGH and BMC oncology clinics. MGH locations will include oncology clinics at MGH main campus, NSMC, NWH, and Waltham MGH.

There are no local site restrictions.

Briefly describe study procedures. Include any local site restrictions, for example, "Subjects enrolled at Partners will not participate in the pharmacokinetic portion of the study." Describe study endpoints.

After a recommendation is made for genetic testing during the initial consultation, a session to complete the DA will be scheduled at the start of the next appointment. At this appointment, the MA will escort the patient to a private area and provide the electronic tablet containing the Decision Aid (DA) and instructions for use. Upon completion of the DA, patients will be asked to indicate their decision about whether to pursue genetic testing and which specific multi-gene panel to pursue. Two copies of the DA summary will be printed out. The patient will keep one copy of the summary sheet and the second will be shared with their MD provider in clinic. No PHI will be entered or stored on the electronic device. The only identifier included will be a User ID. The provider will review the preferences, discuss any questions, document the discussion in the electronic medical record, and proceed with informed consent/genetic testing as per patient preference. The provider will collect the DA printout and store with the study staff. At any time in this process, the patient can elect to defer a decision and request a follow-up appointment with a genetic counselor.

For studies involving treatment or diagnosis, provide information about standard of care at Partners (e.g., BWH, MGH) and indicate how the study procedures differ from standard care. Provide information on available alternative treatments, procedures, or methods of diagnosis.

N/a

Describe how risks to subjects are minimized, for example, by using procedures which are consistent with sound research design and which do not unnecessarily expose subjects to risk or by using procedures already being performed on the subject for diagnostic or treatment purposes.

The risks of this study are expected to be minimal as the patients will be able to decline participation in the DA at any timepoint.

Describe explicitly the methods for ensuring the safety of subjects. Provide objective criteria for removing a subject from the study, for example, objective criteria for worsening disease/lack of improvement and/or unacceptable adverse events. The inclusion of objective drop criteria is especially important in studies designed with placebo control groups.

A patient can decline participation at any time.

FORESEEABLE RISKS AND DISCOMFORTS

Provide a brief description of any foreseeable risks and discomforts to subjects. Include those related to drugs/devices/procedures being studied and/or administered/Performed solely for

research purposes. In addition, include psychosocial risks, and risks related to privacy and confidentiality. When applicable, describe risks to a developing fetus or nursing infant.

This is a low risk study. All participants will complete surveys at baseline and post-intervention that assess knowledge, shared decision making, and decisional conflict. There are no physical risks or medical/device side effects involved in the study. All efforts will be made to protect the confidentiality of protected health information. Identifiable information will be stored in a secure, password-protected database. Only authorized study personnel at Massachusetts General Hospital or Boston Medical Center will have access to this information. Further identifiable information may be revealed if necessary to protect the patient from risk or harm. Certain federal and state agencies may also have access if required by law. All staff have completed clinical investigation training that includes a focus on subject confidentiality.

It is possible that patients will feel upset by questions about their risk for an inherited cancer syndrome. We will monitor emotional distress. If this occurs, the clinical research coordinator will inform the PI or genetic counselor, who will provide potential referrals if it is determined that the participant requires and desires further psychological assistance. There are Psychiatry Services or Social Work Departments who provide clinical services to patients, or the genetic counselor can more thoroughly address concerns about inherited cancer risk.

EXPECTED BENEFITS

Describe both the expected benefits to individual subjects participating in the research and the importance of the knowledge that may reasonably be expected to result from the study. Provide a brief, realistic summary of potential benefits to subjects, for example, "It is hoped that the treatment will result in a partial reduction in tumor size in at least 25% of the enrolled subjects." Indicate how the results of the study will benefit future patients with the disease/condition being studied and/or society, e.g., through increased knowledge of human physiology or behavior, improved safety, or technological advances.

A potential benefit to participating in the study is the opportunity to learn more about inherited cancer risk and genetic testing options. In aggregate, the study will define the implementation process and role for decision aids in the pre-test counseling for genetic testing. This approach promises to increase access, communication, and quality decision making for genetic testing. The risks to participation are low. Genetic testing is already part of routine care, and the focus of this study is to develop a new strategy for effective education and decision-making prior to genetic testing.

EQUITABLE SELECTION OF SUBJECTS

The risks and benefits of the research must be fairly distributed among the populations that stand to benefit from it. No group of persons, for example, men, women, pregnant women, children, and minorities, should be categorically excluded from the research without a good scientific or ethical reason to do so. Please provide the basis for concluding that the study population is representative of the population that stands to potentially benefit from this research.

The study population is representative of the population seen in the MGH and BMC oncology clinics for treatment of ovarian cancer and pancreatic cancer.

When people who do not speak English are excluded from participation in the research, provide the scientific rationale for doing so. Individuals who do not speak English should not be denied participation in research simply because it is inconvenient to translate the consent form in different languages and to have an interpreter present.

Non-English speakers are not the targeted population of this study. If English is not the primary language for an eligible subject, we will use medical interpreters to guide patients through the decision aid or translate the decision aid into other languages.

For guidance, refer to the following Partners policy:

Obtaining and Documenting Informed Consent of Subjects who do not Speak English

<https://www.partners.org/Assets/Documents/Medical-Research/Clinical-Research/Non-English-Speaking-Subjects.pdf>

RECRUITMENT PROCEDURES

Explain in detail the specific methodology that will be used to recruit subjects. Specifically address how, when, where and by whom subjects will be identified and approached about participation. Include any specific recruitment methods used to enhance recruitment of women and minorities.

All patients seen in the MGH and BMC oncology clinics with ovarian or pancreatic cancer who are referred for genetic testing will be invited to participate by their oncologist. If the patient is interested in learning more about the decision aid at the end of their appointment, the oncologist will take them to another exam room where they can discuss the study with a study coordinator. If the patient agrees to participate, the study coordinator will schedule the DA for the beginning of the patient's next clinic appointment and provide the DA Study Fact Sheet for the patient to review.

Institutions will register eligible participants in the Clinical Trials Management System (CTMS) OnCore as per DF/HCC Policy REGIST-101

Provide details of remuneration, when applicable. Even when subjects may derive medical benefit from participation, it is often the case that extra hospital visits, meals at the hospital, parking fees or other inconveniences will result in additional out-of-pocket expenses related to study participation. Investigators may wish to consider providing reimbursement for such expenses when funding is available

A small monetary incentive (\$10) will be offered to participants for completion of the post-decision aid study survey.

For guidance, refer to the following Partners policies:

Recruitment of Research Subjects

<https://www.partners.org/Assets/Documents/Medical-Research/Clinical-Research/Recruitment-Of-Research-Subjects.pdf>

Guidelines for Advertisements for Recruiting Subjects

<https://www.partners.org/Assets/Documents/Medical-Research/Clinical-Research/Guidelines-for-Advertisements.pdf>

Remuneration for Research Subjects

<https://www.partners.org/Assets/Documents/Medical-Research/Clinical-Research/Remuneration-for-Research-Subjects.pdf>

CONSENT PROCEDURES

Explain in detail how, when, where, and by whom consent is obtained, and the timing of consent (i.e., how long subjects will be given to consider participation). For most studies involving more than minimal risk and all studies involving investigational drugs/devices, a licensed physician investigator must obtain informed consent. When subjects are to be enrolled from among the investigators' own patients, describe how the potential for coercion will be avoided.

When eligible subjects come in for their next oncology clinic appointment, they will be met by a study coordinator at check-in. The coordinator will go over the DA Study Fact Sheet with them, giving ample time for subjects to ask questions. Subjects will then be provided with a tablet to complete the DA survey. Informed consent will be implied if the patient completes the survey.

NOTE: When subjects are unable to give consent due to age (minors) or impaired decision-making capacity, complete the forms for Research Involving Children as Subjects of Research and/or Research Involving Individuals with Impaired Decision-making Capacity, available on the New Submissions page on the PHRC website:

<https://partnershealthcare.sharepoint.com/sites/phrmApply/aieipa/irb>

For guidance, refer to the following Partners policy:

Informed Consent of Research Subjects:

<https://www.partners.org/Assets/Documents/Medical-Research/Clinical-Research/Informed-Consent-of-Research-Subjects.pdf>

DATA AND SAFETY MONITORING

Describe the plan for monitoring the data to ensure the safety of subjects. The plan should include a brief description of (1) the safety and/or efficacy data that will be reviewed; (2) the planned frequency of review; and (3) who will be responsible for this review and for determining whether the research should be altered or stopped. Include a brief description of any stopping rules for the study, when appropriate. Depending upon the risk, size and complexity of the study, the investigator, an expert group, an independent Data and Safety Monitoring Board (DSMB) or others might be assigned primary responsibility for this monitoring activity.

NOTE: Regardless of data and safety monitoring plans by the sponsor or others, the principal investigator is ultimately responsible for protecting the rights, safety, and welfare of subjects under his/her care.

The PI, [name], will act as the chief Data and Safety Monitoring Officer for all proposed research. The potential risks are minimal as this is a survey study and there are no physical or medication interventions. Monthly reports on collected data will be generated by study staff, and any issues will be reported to the Principal Investigator (PI) and dealt with accordingly. The PI will supervise data and safety monitoring at all levels. He will determine when research needs to be altered or stopped.

Describe the plan to be followed by the Principal Investigator/study staff for review of adverse events experienced by subjects under his/her care, and when applicable, for review of sponsor safety reports and DSMB reports. Describe the plan for reporting adverse events to the sponsor and the Partners' IRB and, when applicable, for submitting sponsor safety reports and DSMB reports to the Partners' IRBs. When the investigator is also the sponsor of the IND/IDE, include the plan for reporting of adverse events to the FDA and, when applicable, to investigators at other sites.

NOTE: In addition to the adverse event reporting requirements of the sponsor, the principal investigator must follow the Partners Human Research Committee guidelines for Adverse Event Reporting

[name] will be responsible for reporting any unanticipated problems, including adverse events, to the PHRC. The PI will report any unanticipated problems within 5 working days/7 calendar days of the date at which the PI first becomes aware of the problem during the conduct of the study, after study completion, or after subject withdrawal or completion. Although this proposed project is perceived to be relatively low-risk, the study may be terminated by [name] if the frequency of serious or unexpected adverse events is higher than that anticipated. Once this determination is made, a

memo will be sent to the IRB and to NIH explaining the reasons for the determination.

MONITORING AND QUALITY ASSURANCE

Describe the plan to be followed by the principal investigator/study staff to monitor and assure the validity and integrity of the data and adherence to the IRB-approved protocol. Specify who will be responsible for monitoring, and the planned frequency of monitoring. For example, specify who will review the accuracy and completeness of case report form entries, source documents, and informed consent.

NOTE: Regardless of monitoring plans by the sponsor or others, the principal investigator is ultimately responsible for ensuring that the study is conducted at his/her investigative site in accordance with the IRB-approved protocol, and applicable regulations and requirements of the IRB.

[name] will oversee all data collection and ensure that it is stored in a confidential and secure manner consistent with all regulatory requirements. Formal monthly meetings focusing on data collection and storage will be held with all the research staff, and a Data Monitoring Committee (PI, [name] (Co-Investigator), [name] (Co-investigator), [name] (Co-Investigator)) will meet quarterly.

For guidance, refer to the following Partners policies:

 Data and Safety Monitoring Plans and Quality Assurance

<https://www.partners.org/Assets/Documents/Medical-Research/Clinical-Research/DSMP-in-Human-Subjects-Research.pdf>

 Reporting Unanticipated Problems (including Adverse Events)

<https://www.partners.org/Assets/Documents/Medical-Research/Clinical-Research/Reporting-Unanticipated-Problems-including-Adverse-Events.pdf>

PRIVACY AND CONFIDENTIALITY

Describe methods used to protect the privacy of subjects and maintain confidentiality of data collected. This typically includes such practices as substituting codes for names and/or medical record numbers; removing face sheets or other identifiers from completed surveys/questionnaires; proper disposal of printed computer data; limited access to study data; use of password-protected computer databases; training for research staff on the importance of confidentiality of data, and storing research records in a secure location.

NOTE: Additional measures, such as obtaining a Certificate of Confidentiality, should be considered and are strongly encouraged when the research involves the collection of sensitive data, such as sexual, criminal or illegal behaviors.

The privacy of all subjects will be protected and confidentiality maintained. After enrollment, all subjects will be identified by a unique identification

number. The code key connecting the name of the subject to the identification number will be kept in a separate secure location. No PHI will be entered or stored on the electronic decision aid device. The only identifier will be a User ID.

Personal information along with study data will be kept in REDCap, an online partners sponsored data storage site. Only investigators and study staff will have access to the data stored in password protected computer databases.

SENDING SPECIMENS/DATA TO RESEARCH COLLABORATORS OUTSIDE PARTNERS

Specimens or data collected by Partners investigators will be sent to research collaborators outside Partners, indicate to whom specimens/data will be sent, what information will be sent, and whether the specimens/data will contain identifiers that could be used by the outside collaborators to link the specimens/data to individual subjects.

No specimens or data will be shared with collaborators outside of Partners.

Specifically address whether specimens/data will be stored at collaborating sites outside Partners for future use not described in the protocol. Include whether subjects can withdraw their specimens/data, and how they would do so. When appropriate, submit documentation of IRB approval from the recipient institution.

No specimens or data will be shared with collaborators outside of Partners.

RECEIVING SPECIMENS/DATA FROM RESEARCH COLLABORATORS OUTSIDE PARTNERS

When specimens or data collected by research collaborators outside Partners will be sent to Partners investigators, indicate from where the specimens/data will be obtained and whether the specimens/data will contain identifiers that could be used by Partners investigators to link the specimens/data to individual subjects. When appropriate, submit documentation of IRB approval and a copy of the IRB-approved consent form from the institution where the specimens/data were collected.

Data collected at the BMC site will be de-identified and sent to [name] via Secure file transfer.

Development and Implementation of Electronic Decision Aids for Genetic Testing in Inherited Cancer Syndromes

NCT04704193

July 18th, 2024

The analysis will be descriptive in nature. We will tabulate the responses for all survey items from all participants who completed the survey. The primary outcomes are the 6 items related to participant satisfaction with how educational information is presented in the decision aid, with each rated as poor, fair, good or excellent. The results will be summarized with count and percentage for each response category. The secondary outcome is the amount of time spent on the decision aid, which will be summarized using mean with standard deviation or median with interquartiles if the distribution is skewed.

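### The SAP specifies no tabulation by decision aid, although Aim 1c is to pilot each of two aids with 50 patients planned per tumour type

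*SAP*

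**What the plan says.** The protocol sets out two tools. Under Specific Aims, Aim 1 is "To pilot electronic decision aids for selection of a multi-gene panel", in the plural. Aim 1a is to "Implement our decision aid already completed for ovarian cancer patients", Aim 1b is to "Adapt the decision aid for pancreatic cancer patients", and Aim 1c is to "pilot each tool at two institutions (MGH and BMC) to establish feasibility and acceptability". Recruitment follows the same division; Research Design and Methods states "We plan to enroll 100 patients in total (50 ovarian cancer patients; 50 pancreatic cancer patients").

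The SAP is one paragraph and calls the analysis descriptive. On tabulation it says "We will tabulate the responses for all survey items from all participants who completed the survey". The primary outcomes are six items on "participant satisfaction with how educational information is presented in the decision aid", each on a four-level scale from poor to excellent and summarised by count and percentage per level. "The secondary outcome is the amount of time spent on the decision aid", summarised by mean and standard deviation or, if skewed, by median and quartiles. No grouping by aid, tumour type or site is mentioned, and the protocol does not provide one.

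**The concern.** Aim 1c makes the individual tool the unit to be judged, and enrolment is planned in two equal cohorts to match. The SAP defines one set of survey completers and one summary per outcome. An analyst could follow it exactly, report a single percentage per response level, and leave the question in Aim 1c unanswered.

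The question is a real one because the tools start from different positions: one was already finished, and the other had to be adapted to a different cancer. Whether the adapted aid is received as well as the existing one is something a pilot of each should show. If the adapted aid were rated worse, an overall percentage would average that away. If completion differed between the cohorts, the overall percentage would also lean towards whichever aid had more completers. The same applies to the overall summary of time on the aid.

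**Working it through.** **Inputs from the documents**

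- Two aids, ovarian and pancreatic (Protocol, Specific Aims 1a and 1b).
- Each tool is to be piloted (Specific Aims 1c).
- Planned enrolment of 50 ovarian and 50 pancreatic patients, 100 in all (Research Design and Methods). Check: 50 + 50 = 100, as stated.
- Analysis set: survey completers, with no strata named (SAP).

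The documents give no expected rates, completion figures or precision calculation. The rates below are therefore assumptions, and 50 completers per aid (full completion of planned enrolment) is assumed unless stated otherwise.

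**Step 1. What an overall count leaves open.** Suppose k of 100 completers rate an item good or excellent, with 50 completers per aid and k at least 50. The smallest possible gap between the aids is 0 (k even). The largest occurs when one aid scores 50/50 and the other (k − 50)/50, so

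largest gap = [50 − (k − 50)]/50 = (100 − k)/50.

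| Overall | Most unequal split | Possible gap (points) |
|---|---|---|
| 70/100 | 50/50 and 20/50 | 0 to 60 |
| 80/100 | 50/50 and 30/50 | 0 to 40 |
| 90/100 | 50/50 and 40/50 | 0 to 20 |

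**Step 2. Two less extreme splits with the same overall 80/100** (exact Clopper-Pearson 95% intervals):

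- 40/50 and 40/50: 80% each, interval 66% to 90%.
- 45/50 and 35/50: 90% (78% to 97%) and 70% (55% to 82%).

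The overall table is identical in both cases.

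**Step 3. Dependence on who completes.** Assume rates of 90% for the ovarian aid and 70% for the pancreatic aid. The overall percentage is (n₁ × 0.90 + n₂ × 0.70)/(n₁ + n₂):

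- n₁ = 50, n₂ = 50: (45 + 35)/100 = 80.0%.
- n₁ = 50, n₂ = 25: (45 + 17.5)/75 = 83.3%.
- n₁ = 25, n₂ = 50: (22.5 + 35)/75 = 76.7%.

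The overall figure moves by 83.3 − 76.7 = 6.6 points although neither aid's rate has changed.

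**Step 4. Precision cost of splitting.** Exact 95% interval for an observed 50%, where intervals are widest:

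| | By aid | Overall |
|---|---|---|
| Full completion | 25/50: 35.5% to 64.5% (half-width 14.5 points) | 50/100: 39.8% to 60.2% (10.2 points) |
| Assumed 40 completers per aid | 20/40: 33.8% to 66.2% (16.2 points) | 40/80: 38.6% to 61.4% (11.4 points) |

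**The case against.** The strongest reply is that the SAP leaves the table layout open and does not choose a pooled one. Its sentence says who is counted, and a table with an ovarian and a pancreatic column would comply with every word. The singular reference to the aid is weak evidence of pooling: the protocol uses the same singular where it plainly covers both tumour types, and the SAP's own title is plural. All of this stands. The point is an omission, and it does not rest on the singular wording.

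It can also be said that, with no test, threshold or go/no-go rule, a by-aid table could be added at reporting without harm to error rates. That is true, and it limits the consequence. It also means that specifying the split now has no multiplicity cost, while leaving it out makes the answer to Aim 1c depend on a later choice. In a purely descriptive plan, the grouping of the table is one of the main decisions to be made.

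Third, acceptability is not defined, and the SAP does not label the satisfaction items as its measure. That link is an inference. The items are the plausible measure, and the same gap would affect any other measure taken from this survey.

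Fourth, the bound in Step 1 holds for any factor that divides the sample in half. It shows what the overall figure cannot exclude and says nothing about what is likely. If the aids perform alike, nothing is masked.

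Finally, Aim 1c also names two institutions, so one might ask why not split by site. The wording makes the tool the object of the pilot and the institutions the places where it happens. The planned cohort sizes are given by tumour type and not by site. The argument for a split by aid is therefore the direct one.

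**Conclusion.** The concern holds. The protocol sets out to pilot each of two aids and plans 50 patients for each tumour type; the SAP specifies a summary over survey completers with no tabulation by aid, and nothing elsewhere fills the gap. An overall-only report would comply with the plan and not show how each tool did. At an overall 80/100 it would be compatible with anything from no difference to 40 points, assuming 50 completers per aid.

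The omission is certain from the text; the size of any real difference between the aids is unknown. The effect is confined to reporting: no inference is invalid and the sample size need not change. It should be corrected because a stated aim has no matching output.

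**What to change.** Add to the SAP a statement that the six primary items and time on the aid will be summarised separately for the ovarian aid and the pancreatic aid, beside an overall column. Give the number enrolled and the number completing for each aid, so that each percentage has its own denominator and the weight of each aid in the overall figure is visible. Keep the presentation descriptive, with no test between aids.

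The cost is one sentence and two extra table columns. The grouping is the one the study already recruits by, so no new data should be needed. This assumes that tumour type is carried in the analysis file, including the de-identified data sent from BMC; the documents do not list the fields. The price is the wider by-aid intervals in Step 4, and the overall column keeps the more precise combined figure.

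### Does naming language help only for the decision aid, and not for the survey, leave patients who need it out of the satisfaction results?

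*SAP*

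**What the plan says.** The SAP is a single descriptive paragraph. On outcomes it says "The primary outcomes are the 6 items related to participant satisfaction with how educational information is presented in the decision aid", each rated on a four-level scale. On the analysis set it says "We will tabulate the responses for all survey items from all participants who completed the survey", and on the summary "The results will be summarized with count and percentage for each response category". Time spent on the aid is the secondary outcome, and no denominator is given for it.

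The protocol touches on language and on surveys in several places:

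- Equitable Selection of Subjects: people who do not speak English are not the group the study is aimed at, but for an eligible patient with another main language, "we will use medical interpreters to guide patients through the decision aid or translate the decision aid into other languages".
- Research Design and Methods: "Patients who are unable to complete surveys will be excluded from this study". Language is not mentioned.
- Foreseeable Risks and Discomforts: "All participants will complete surveys at baseline and post-intervention that assess knowledge, shared decision making, and decisional conflict". Satisfaction is not listed.
- Recruitment Procedures: a $10 incentive "will be offered to participants for completion of the post-decision aid study survey".
- Consent Procedures: the patient is handed a tablet to complete what is called the DA survey, and "Informed consent will be implied if the patient completes the survey".

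**The concern.** The commitment on language mentions the aid and stops there. The incentive is tied to a survey that comes after the aid, which suggests a separate instrument. Survey completion then matters three times: for eligibility, for implied consent and for entry into the primary analysis. On a literal reading, a patient could be guided through the aid by an interpreter and still be ineligible, or absent from the six items, because the survey is in English. The SAP plans no comparison of aid users with survey completers, so a reader of the percentages might not see the loss.

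First among the Specific Aims is a pilot meant to show whether the tool is feasible and acceptable. If patients who used it with help were missing, the satisfaction percentages would describe a narrower group than the one that received it. Time on the aid could also be summarised over a different set of patients from the ratings.

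**Working it through.** **What the concern needs, set against the text**

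1. *The six items must sit in a separate survey that gets no language help.* The SAP says only that there is a survey. Foreseeable Risks and Discomforts lists survey content without satisfaction. Recruitment Procedures points to a survey after the aid. Consent Procedures describes a survey done on the tablet, and Research Design and Methods says the tablet holds the aid. A separate survey is a reasonable inference; a single tablet session, with the interpreter present throughout, is another. The text does not settle it.
2. *The exclusion must reach language.* The exclusion sentence does not mention language. The Equitable Selection section answers a form question about leaving non-English speakers out of research, and its answer is to accommodate them. Taking the exclusion to mean inability despite the planned help makes the two sections agree.
3. *The loss must be invisible.* The SAP reports counts as well as percentages, so the number of responders will be shown. Recruitment Procedures has eligible participants registered in the trials management system, so a number to compare it with exists. What is absent is a planned split by language or mode of delivery.

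**Size, under assumptions**

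From the documents: N = 100 planned (50 ovarian + 50 pancreatic = 100, which agrees). There is no power or precision calculation to reproduce.

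Assumed, not in the documents: a share s needs language help; none of them completes the survey; 90% of completers rate an item good or excellent.

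- Completers = 100(1 − s)
- Lowest possible percentage among all users = 90(1 − s)
- Highest possible = 90(1 − s) + 100s
- If 70% of the missing would have been favourable: 90(1 − s) + 70s

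| s | Completers | Range for all users | With 70% among the missing |
|---|---|---|---|
| 2% | 98 | 88.2–90.2% | 89.6% |
| 5% | 95 | 85.5–90.5% | 89.0% |
| 10% | 90 | 81–91% | 88.0% |
| 20% | 80 | 72–92% | 86.0% |

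For scale, the 95% sampling half-width of a 90% rating among 90 completers is 1.96 × √(0.9 × 0.1 / 90) = 0.062, or 6.2 points. The 2-point shift at s = 10% is about a third of that. The 9-point extreme (90 − 81) needs every missing patient to be unfavourable. These bounds hold for non-completion of any cause; nothing in them is particular to language.

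**The case for a change.** The strongest case for a change is that percentages are the whole result of a descriptive pilot, so their denominator deserves a sentence. The protocol chose to admit patients with another main language, and having admitted them it should account for them. That an interpreter would stay for the survey is a guess about practice, and two institutions might differ. Even if the six items are inside the aid, the restriction to completers and the lack of a planned count of aid users come straight from the SAP. The cost would be a sentence or two.

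Part of this stands. It is true that neither document extends language help to the survey in words, that the SAP plans no count of aid users beside completers, and that time on the aid has no stated denominator. A sentence on each would be a reasonable courtesy. What does not stand is the step from unstated to lost. Specific Aims has the study write standard operating procedures for implementation at both institutions, which is the natural place for how long an interpreter stays. Numbers enrolled and numbers responding are items an analyst would ordinarily report without instruction. A breakdown by mode of delivery would rest on small counts and be imprecise.

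**Conclusion.** No change to the plan is needed. The wording leaves a detail open, and the conclusion that patients needing language help are excluded or lost from the primary outcome is drawn from silence; no stated rule is shown to give a wrong result. The supposed conflict between the exclusion sentence and the language provision disappears on the ordinary reading of both.

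The effect cannot be sized from the documents. Under the assumptions above (no assisted patient completes the survey, 90% favourable among completers, 70% among the missing) the shift is 0.4 points if 2% need help, 2 points if 10% do and 4 points if 20% do. The higher shares are harder to credit in a study that says it is not aimed at non-English speakers. No test, sample size or decision threshold depends on the result. The view would change if it emerged that the survey was offered in English only and that assisted patients were more than a handful.
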